1.8 Abbreviations

SHEAP	Statistical and Health Economics Analysis Plan
MSK	Musculoskeletal
CCG	Clinical Commissioning Group
CSI	Corticosteroid Injection
CSI & HD	Corticosteroid injection with hydrodilatation
OSS	Oxford Shoulder Score
EQ-5D-5L	European Quality of Life 5 Dimensions 5 Level Instrument
EQ-5D-3L	European Quality of Life 5 Dimensions 3 Level Instrument
ROM	Range of motion
SD	Standard Deviation
IQR	Interquartile Range
AE	Adverse Event
SAE	Serious Adverse Event
IE	Intercurrent Event
CCA	Complete case analysis
SI	Single imputation
MI	Multiple imputation
CI	Confidence interval
AUC	Area under the curve

2. Background and trial design

Study objectives	
To determine the feasibility of an adequately powered definitive trial we will assess:
 
 • The rate of eligible participants presenting to the MSK hubs. • The proportion of eligible participants that clinicians are willing to recruit. • The proportion of eligible participants that are randomised. • Adherence to the study protocol and retention at 6 months. • Data completeness using traditional clinical reporting forms and routine data sources. • Data concordance between traditional clinical reporting forms and routine data sources • Estimand for a definitive trial
Study design	Primary research – Multi-centre, individually-randomised controlled feasibility interventional trial
Setting	
A total of four Musculoskeletal (MSK) Hubs: Three located within Tower Hamlets, Newham and Waltham Forest (TNW) collaborative of Clinical Commissioning Group (CCG). One in Norfolk (East Coast Community Care C.I.C and James Paget Hospitals NHS Foundation Trust).

Participants	
Inclusion Criteria:
 
 • Adults with frozen shoulder • Aged 18 years and older • Loss of passive external rotation of at least 50% compared with the contralateral side • Plain radiographs demonstrating the absence of glenohumeral osteoarthritis or other pathology 
Exclusion Criteria:
 
 • Recurrent ipsilateral frozen shoulder • Presentation following breast cancer or local radiotherapy • Known Rotator cuff tear • Long term systemic corticosteroid use or previous ipsilateral shoulder injection within 12 months

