Interventions	
Usual care group Corticosteroid injection (CSI): with the patient in a lateral decubitus position and via a posterior approach, using an aseptic technique a needle will be inserted into the glenohumeral joint under ultrasound guidance. 3ml of 1% lignocaine, 3ml 0.25% bupivacaine and 80mg depomedrone will be infiltrated into the joint.
 
Intervention Group Corticosteroid injection with hydrodilatation (CSI & HD): with the patient in a lateral decubitus position and via a posterior approach, using an aseptic technique a needle will be inserted into the

	
glenohumeral joint under ultrasound guidance. 10ml of 1% lignocaine, 5ml 0.25% bupivacaine 80mg depomedrone and between 5 and 20ml of sterile normal saline will be injected into the glenohumeral joint under ultrasound guidance visualising the posterior capsule. The volume of fluid will be used to create capsular distention. Once capsular collapse/decompression occurs, injection of saline ceases. Injection of saline also ceases if the procedure is poorly tolerated. The total volume of injection is recorded. A minimum total of 20ml of fluid will be used to confirm a hydrodilatation has taken place.

Feasibility outcomes
	
 • The rate of eligible participants presenting to the MSK hubs per month. • The proportion of eligible participants that clinicians are willing to recruit. • The proportion of eligible participants that are randomised. • Participant adherence to study protocol • Retention at 6 months follow-up • Data completeness • Concordance of primary care and hospital care data collected with case report forms against routinely collected linked data

3. Outcome measures

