3.1 Feasibility outcomes

The feasibility outcomes measured are:

Recruitment

- The average rate of eligible participants presenting to MSK hubs per month:
 - o No. of eligible participants presenting to MSK hubs during recruitment period/ length of recruitment period (in months)
- Proportion of eligible participants clinicians willing to recruit (see appendix 2 for more detail):
 - o No. of eligible participants clinicians willing to recruit/ no. of eligible participants presented to MSK hubs
- Proportion of eligible participants that are randomised:
 - o No. of eligible participants randomised/ no. of eligible participants presented to clinicians.

Adherences

- Participant adherence to study protocol:
 - o No. of participants receiving injections / no. of randomised participants

Retention

- General retention:
 - o No. of participants who provided any follow-up data / no. of randomised participants for study visits listed in section 3.2, overall and by treatment groups
- Oxford Shoulder Score (OSS) questionnaire retention:
 - No. of participants who answered any OSS items / no. of randomised participants for study visits listed in section 3.2, overall and by treatment groups

Data completeness

- Proportion of missingness in each outcome at each time point (as specified in section 3.2), overall and by reasons of missingness (where available):
 - o No. of participants who provided complete outcome (usable in analysis without imputation)/ no. of randomised participants
- Proportion of randomised participants who returned resource use questionnaire, by study visits, overall and by reason of missingness (where available):
 - o No. of randomised participants who returned resource use questionnaire/ no. of randomised participants for study visits listed in section 3.2 where such a questionnaire is due
- Proportion of randomised participants who were successfully linked to administrative primary care records
 - o No. of randomised participants successfully linked to administrative primary care records/ no. of randomised participants
- Proportion of randomised participants who were successfully linked to administrative hospital care records
 - o No. of randomised participants successfully linked to administrative hospital care records/ no. of randomised participants

Concordance of health care data collected with case report forms against routinely collected linked data

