- Proportion of discrepancy in demographic variables (age, gender, ethnicity, smoking history, and alcohol history) between routinely collected linked data and data collected with case report forms
 - o No. of participants with inconsistent answers/ no. of randomised participants with available linked data, by demographic variables of interest
- Proportion of participants with reported resource use
 - o No. of participants with reported resource use / no. of randomised participants with returned or linked data for resource use categories listed in section 3.2, by study visit
- Rate of resource use per participant
 - o No. of resource use items (consultations, medications)/ no. of randomised participants with returned or linked data for resource use categories listed in section 3.2, by study visit

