	Proportion with reported resource use	No. with reported resource use /no. of randomised participants with returned or linked data for resource use categories listed in section 3.2, by study visit
	Rate of reported resource use	No. of reported resource use items (consultations, medications)/ no. of randomised participants with returned or linked data for resource use categories listed in section 3.2, by study visit

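### Resource-use concordance is specified only as marginal proportions and rates, which cannot show whether form and routine data agree for the same participant

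*SAP*

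**What the plan says.** The study objectives in SAP section 2 include "Data concordance between traditional clinical reporting forms and routine data sources". The feasibility outcomes in the same section list "Concordance of primary care and hospital care data collected with case report forms against routinely collected linked data", and section 3.1 repeats this as a heading: "Concordance of health care data collected with case report forms against routinely collected linked data".

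Three measures stand under that heading:

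- **Demographics:** "No. of participants with inconsistent answers/ no. of randomised participants with available linked data, by demographic variables of interest". This compares the two sources within a person.
- **Proportion using resources:** "No. of participants with reported resource use / no. of randomised participants with returned or linked data", by resource category and study visit.
- **Rate of resource use:** "No. of resource use items (consultations, medications)/ no. of randomised participants with returned or linked data", on the same basis.

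The data concordance rows of section 5.2.1 restate the resource-use definitions almost unchanged, for example "No. with reported resource use /no. of randomised participants with returned or linked data", and add no agreement statistic. Section 5.2 otherwise provides only means, medians and percentages. Section 3.2 lists eight resource categories, labels them as being for the concordance analyses, and schedules them at four visits (baseline and 6, 12 and 26 weeks). The only concordance dummy table, Table 2, covers baseline variables. No dummy table shows resource use by source.

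**The concern.** Concordance asks whether two sources give the same answer for the same person. The two resource-use measures are group summaries, and neither pairs a participant's questionnaire with that participant's record. The word *or* in the denominator leaves two readings: one pooled figure over anyone with either source, or a separate figure for each source. Neither yields agreement.

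The plan uses paired comparison where it clearly intends agreement. Demographics are checked person by person, and section 5.2.2 assesses self-measured against clinician-measured range of motion with Bland-Altman differences. Resource use is the exception.

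What is at stake is the objective itself. Similar percentages from the two sources could be reported as good concordance while the sources identify different people as users.

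**Working it through.** The SAP states no figure for resource-use concordance, so there is nothing to reproduce. The check asks how much agreement the specified statistics can pin down.

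**Set-up.** For one category at one visit, take N participants with both sources. Let a = use in both, b = form only, c = linked only, d = neither.

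- Difference in marginal proportions = (b - c)/N.
- Observed agreement = (a + d)/N = 1 - (b + c)/N.
- Kappa = (observed - chance)/(1 - chance), where chance agreement is the product of the two *yes* margins plus the product of the two *no* margins.

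The margins fix b - c but not b + c. They show net disagreement but not its total.

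**Example (assumed counts).** N = 50, with 20 users in each source, so the plan reports 40% and 40%. Chance agreement = 0.4 x 0.4 + 0.6 x 0.6 = 0.52.

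| a, b, c, d | Observed agreement | Kappa |
|---|---|---|
| 20, 0, 0, 30 | 50/50 = 1.00 | (1.00 - 0.52)/0.48 = 1.0 |
| 8, 12, 12, 18 | 26/50 = 0.52 | (0.52 - 0.52)/0.48 = 0 |
| 0, 20, 20, 10 | 10/50 = 0.20 | (0.20 - 0.52)/0.48 = -0.67 |

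**Range at the planned sample size.** N = 66 is from section 4.1; it assumes every participant has both sources. The numbers of users, m in each source, are assumptions. With equal margins, a can lie anywhere from max(0, 2m - N) to m, and agreement is 1 - 2(m - a)/N.

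| Users in each source | Lowest agreement | Lowest kappa | Highest agreement and kappa |
|---|---|---|---|
| 33/66 (50%) | 0/66 = 0% | -1.00 | 100%, 1.00 |
| 20/66 (30%) | 26/66 = 39% | -0.43 | 100%, 1.00 |
| 13/66 (20%) | 40/66 = 61% | -0.25 | 100%, 1.00 |

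**What the *or* denominator hides.** With return proportion r and linkage proportion l, the number with both sources lies between (r + l - 1) x 66 and min(r, l) x 66. The rates are assumed:

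- 85% and 85%: 0.70 x 66 = 46.2 to 0.85 x 66 = 56.1.
- 70% and 70%: 0.40 x 66 = 26.4 to 0.70 x 66 = 46.2.

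In both cases the number with either source could be all 66. Figures calculated per source could therefore rest partly on different people, and a gap between them would mix recording differences with who returned a form and who could be linked.

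**The rate.** The same reasoning applies. Equal mean numbers of items in the same people imply only that within-person differences average zero, and say nothing about their spread.

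**The case against.** The best defence is that per-source margins are informative. In the same people, unequal margins reveal net over- or under-recording, and because section 5.3 summarises costs as group means, a net difference in average use is relevant. This stands: a reader might infer that the listed statistics say nothing about concordance, and that goes too far. They are incomplete, because equal margins cannot demonstrate agreement.

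A reader might also infer that the demographic measure understates discrepancy, because its denominator would include people whose value is blank. The SAP does not support this. The definition, "No. of participants with inconsistent answers/ no. of randomised participants with available linked data, by demographic variables of interest", and the row-by-row layout of Table 2 allow a denominator specific to each variable. The plan also does not say how a blank is classed, and counting blanks as inconsistent would raise the figure.

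A third inference would be that the result decides whether routine data replace questionnaires in the full trial. The SAP states no such rule, and section 6.6 plans the full trial from standard deviations, retention, data availability and recruitment.

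Finally, eight categories at four visits give sparse tables. Rare categories such as shoulder surgery may leave kappa unstable or undefined, and standard limits of agreement suit skewed counts poorly. This limits the choice of summary. It does not remove the need to pair the data.

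**Conclusion.** The concern holds for resource use under either reading of the denominator. A stated objective has no specified statistic that can show within-person agreement, and nothing elsewhere in the SAP supplies one. The size depends on how common use is. With equal margins among 66 paired participants, the lowest compatible agreement is 0% at 50% use, 39% at 30% and 61% at 20%, against a maximum of 100% each time. The prevalences and the return and linkage rates behind these ranges are illustrative, since the SAP gives none; the algebra does not depend on them.

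The gap is confined to one descriptive feasibility outcome. It does not touch the treatment comparison, randomisation, safety reporting or sample size. The demographic denominator is an ambiguity to clarify, not a demonstrated bias.

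**What to change.** In sections 3.1 and 5.2.1, for each resource category and visit:

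1. Restrict the concordance analysis to participants with both a returned questionnaire and linked data, and state that number.
2. Report the four counts (both, form only, linked only, neither) with percent agreement. Add kappa with a 95% CI only where cells are not too sparse.
3. Summarise the within-person difference between sources in number of items.
4. Keep the present proportions and rates as description, labelled by source, each with its own denominator.

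For demographics, add a sentence stating that the denominator counts participants with non-missing values in both sources.

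The cost is SAP wording and a short analysis, with no new data collection. The paired subset will be smaller than the present denominator. There will be up to 8 x 4 = 32 cross-tabulations, which fit in one compact layout with a row per category and visit and columns for the four counts and percent agreement.

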3.2 Clinical and health economics endpoints

These are the proposed outcome measures for use in a full trial; feasibility of collection will also be assessed (see 3.1 and 5.2.1).

These outcomes will be collected according to the following schedule.

Study intervention	Baseline Visit 1	Intervention Visit 2	6 Weeks Visit 3	12 Weeks Visit 4 (remote)	26 Weeks Visit 5 (remote)
Timeframe	-0 to +/- 1 week	+/-3 to +/- 5 days	+/- 3 weeks	- 3/ +7 weeks	-7 weeks to end of follow-up
Demographic information for concordance analyses: 
 - Age - Gender - Ethnicity - Smoking history - Alcohol history 	x				
Oxford Shoulder Score (OSS)	x		x	x	x
Range of Motion (ROM)	x		x	x	x
EQ-5D-5L	x		x	x	x
Resource Use Questionnaire	x		x	x	x
Participant Experience Questionnaire					x
Resource Use categories in concordance analyses: 
 - Shoulder surgery - Consultation with orthopaedics, radiology or other hospital specialist 	x		x	x	x

 - NHS hospital physiotherapy or occupational therapy - Consultation with GP - Consultation with nurse in primary/community care - NHS community physiotherapy, occupational therapy - Prescribed medication 
Additional shoulder injection (outside study)
					
--	--	--	--	--	--

Upper limb function – Oxford Shoulder Score

Upper limb function will be assessed using the Oxford Shoulder Score (OSS). The OSS is a validated patient self-reported instrument developed with patients, including those with frozen shoulder¹; it has been used in randomised trials of patients with frozen shoulder and in long-term follow-up studies.²

The OSS is a 12-item measure, where each item is scored from 0 (worst/most severe) to 4 (best/fewest symptoms). The 12 items are then summed to give a total score between 0 and 48, where a lower score indicates a higher degree of disability.^{1,3} OSS is the proposed primary outcome for the definitive trial.

Health-related quality of Life

Health-related quality of life will be assessed using the EuroQol 5 dimensions instrument (EQ-5D-5L)⁴; a valid measure of health-related quality-of-life, consisting of a five-dimension health status classification system (where the lowest level of severity is coded 1 and the highest 5) and a separate visual analogue scale ranging from 0 to 100, with 100 indicating “the best health you can imagine” and 0 indicating “the worst health you can imagine.” VAS score shows the patient’s perceived overall health and requires no further derivation.

Overall QoL utility scores will be derived for all contributing study participants’ quality of life assessments using the UK National Institute for Health and Care Excellence (NICE) decision support unit EQ-5D scoring algorithm⁵. The estimation algorithm will directly map from individual-specific, EQ-5D-5L, health states to individual-specific, EQ-5D-3L, utility scores, using age and gender as necessary covariates⁵. The Stata command eq5dmap will be used to derive the utility scores. Estimated, individual-specific, EQ-5D-3L utility scores will be used as the outcome during statistical analysis. The overall score of the EQ-5D-3L index ranges from -0.594 to 1.000 (i.e., higher scores correspond to a better quality of life).

Upper limb range of motion: forward flexion

Active range of forward flexion is measured between 0-180 degrees, where higher degrees indicate higher mobility of the joint.

The participant will use self-reported charts to self-measure their active range of forward flexion. Research team will also be asked to estimate the participant’s specific range of motion using photographs provided by the participant.

Written instructions and images of how to complete the motion of forward flexion will be provided to the participant. The individual will move their limb into the desired location for measurement and take a photograph. The photograph will be emailed to the research team which will estimate their ROM. This method will allow for collection of data where follow-ups are conducted remotely and telephone if required. The method of participants self-reporting ROM on a chart is currently employed for data collection within the PROFHER-2 Trial (HTA 16/73/03). This will be validated against their OSS score and where patients are reviewed in the MSK hub as part of the routine care with clinician measures of ROM.

Upper limb range of motion: external rotation

Active range of external rotation is measured between 0-90 degrees, where higher degrees indicate higher mobility of the joint.

The ROM is collected and estimated using the same methods described above for forward flexion.

4. Sample size and randomisation

4.1 Sample size calculation

There is no agreed procedure for estimating appropriate sample sizes in feasibility studies. Guidelines suggest recruiting 50-70 participants.^{6,7} Correspondingly, we have selected a convenience sample of 66 participants to determine our ACCORD Protocol version 3.0, 18 November 2022 Page 23 of 32 feasibility objectives. The 95% confidence interval (CI) for a rate estimated to answer a feasibility objective would be at most +/-12.2% wide with a sample size of n=66.

We expect 10 people per month to be diagnosed with frozen shoulder in each MSK Hub. If 25% of these are ineligible and half of the remaining consent to participate in the study, we expect to be able to recruit 2-4 participants per month per site and therefore the convenience sample of 66 participants within 6 months. If these rates were confirmed, we would be able to recruit the required definitive trial sample (anticipated number including attrition=448) within approximately 14 months from 8 Hubs, based upon a recruitment rate of 4 per centre per month and an attrition estimate of 15%.

4.2 Randomisation procedure

Randomisation will only occur when the research team confirms eligibility, and the participant has provided written, informed consent.

Participants will be randomised in a 1:1:1:1 ratio, stratified by recruiting centre, to one of the following:

- CSI&HD and patient to self-measure ROM self-measured before 6 week (+/- 3 days) visit
- CSI&HD and patient to self-measure ROM self-measured after 6 week (+/- 3 days) visit
- CSI alone and patient to self-measure ROM self-measured before 6 week (+/- 3 days) visit
- CSI alone and patient to self-measure ROM self-measured after 6 week (+/- 3 days) visit

The allocation will be determined just prior to the time of the injection, using a web-based, distant randomisation service administered by the Pragmatic Clinical Trials Unit, QMUL. Allocation lists using random permuted blocks of sizes 4 and 8 will be prepared by the trial statistician with the final lists being uploaded to the randomisation system by an independent statistician.

The clinician providing the injection will contact a member of the research team once the participant has arrived for their appointment. The research team member who is appropriately and sufficiently trained and delegated to complete randomisation will randomise the patient and communicate the allocation to the treating clinician.

4.3 Blinding

Participants will be blinded to the allocated treatment. It is not possible to blind the practitioners giving the injection, however, the outcome assessor at the 6 weeks face to face follow-up assessment will be blinded. The trial management group and the trial steering committee will not see results broken down by treatment arm during the trial. No formal testing of the blinding will be performed.

5. Analysis methods

5.1 Baseline characteristics

Baseline characteristics will be summarised for each treatment group, using mean (SD) and median (IQR) for continuous variables and n (%) for categorical variables.

The baseline variables are:

- Oxford Shoulder Score (OSS)
- Quality of life will be assessed using the Euroqol (EQ-5D-5L)
- Upper limb range of motion (ROM) – forward flexion
- Upper limb range of motion (ROM) – external rotation
- Demographic questions:
 - Age
 - Gender
 - Ethnicity
- Baseline characteristics:
 - Medical history
 - Duration of shoulder pain
 - Smoking and alcohol history

